2.2.2. Secondary outcome

Secondary outcomes include:

- Changes in white cells blood sub-population defined by the difference between two time points: the day before adjuvant RT (day -1) to day 28 (+/- 3 days) after RT.

In particular, we will evaluate changes of:

- circulating T cells CD3+CD8+ and CD3+CD4+

- absolute lymphocyte count (ALC) and neutrophil counts (ANC) and neutrophil/lymphocyte ratio (NLR)
- Treg lymphocytes, defined as CD4+CD25+FOXP3+ or CD4+CD25hi+CD39+ cells.
- Naïve/Memory T lymphocytes CD4+ and CD8+ (defined as CD45RA/CD45RO)
- myeloid-derived suppressor cells, defined as cells expressing Lin-neg (CD3, CD14, CD15, CD19, CD56) /HLA-DR-/CD33+/CD11b+ in either a “lymphocyte” (small FSCxSSC) gate, or in a “monocyte” (larger FSCxSSC) gate, and as HLA-DR+/lo CD14+ cells in a large gate.
- Plasmacytoid Dendritic Cells (CD303+CD123+)
- NK cells dim (CD3-CD16+CD56+) and bright (CD3-CD16-CD56++);
- NKT cells (CD3+CD56+);
- Myeloid Dendritic cells (CD1c+ and CD141+);
- Monocytes subsets (classical CD14+CD16-, intermediate CD14+CD16+, non classical CD14+/-CD16+);
- B lymphocytes (CD19)
- Analysis of plasma cytokines (TNFalpha, TGFbeta, IL-6, IL-10) by ELISA;
- IFN signature: real-time PCR on mRNA from peripheral blood mononuclear cells (PBMCs)

- DFS of patients according to the values of the above reported immune population at baseline, after RT and according to the changes before/after RT

- Changes in immune population cell at the two time points according to the following variables:

- Site of irradiation (involving or not nodal basins, head and neck vs non-head and neck area and lymphnodes levels involved in CTV-HR vs CTV-LR)
- Volume of irradiation (expressed as cc) for primary site and nodal basin (volume received by lymphnodes classified as CTV-HR vs CTV-LR)
- Dose of irradiation (total dose received in Gy) for primary site (depending on the margin status) and nodal basin (dose received by lymphnodes classified as CTV-HR vs CTV-LR)

- Changes in immune population cells in the immunosuppressed patient subgroup in comparison with non-immunosuppressed patients

- Changes in immune population cells according to RT related toxicities as mucositis and radiodermatitis

- 2-year OS

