3. SUBJECTS TO BE RECRUITED

3.1. Inclusion criteria

1. Age \geq 18 years.
2. Signed written informed consent.
3. Histologically confirmed diagnosis of cSCC
4. cSCC categorized as high risk according to ASTRO Guidelines:
 - close or positive margins that cannot be corrected with further surgery (secondary to morbidity or adverse cosmetic outcome)
 - gross perineural spread, as identified by radiological or pathological assessment
 - disease recurrence after a prior margin-negative resection
 - pathological stage T3 and T4
 - desmoplastic or infiltrative tumors in the setting of chronic immunosuppression
 - at pathological exam, cSCC involving regional lymphnodes, with the exception of a single, small (<3 cm) cervical lymph node harboring carcinoma, without extracapsular extension.
5. cSCC addressed to adjuvant radiotherapy as per clinical practice (a complete post-operative treatment should be administered with 50-54 or 60-66 Gy depending on the margin status)
6. Eastern Cooperative Oncology Group (ECOG) Performance status of 0-2.

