6. ASSESSMENT OF EFFICACY

Blood samples will be collected at two time point to assess immune-modulating effects of adjuvant radiotherapy.

The following blood cells will be assessed at baseline (day -1) before adjuvant RT and at day 28 (+/- 3) after RT completion:

- circulating T cells CD3+CD8+ and CD3+CD4+
- absolute lymphocyte (ALC) count and neutrophil counts (ANC) and neutrophil/lymphocyte ratio (NLR)
- Treg lymphocytes, defined as CD4+CD25+FOXP3+ or CD4+CD25hi+CD39+ cells.
- Naïve/Memory T lymphocytes CD4+ and CD8+ (defined as CD45RA/CD45RO)
- myeloid-derived suppressor cells, defined as cells expressing Lin-neg (CD3, CD14, CD15, CD19, CD56) /HLA-DR-/CD33+/CD11b+ in either a “lymphocyte” (small FSCxSSC) gate, or in a “monocyte” (larger FSCxSSC) gate, and as HLA-DR+/lo CD14+ cells in a large gate.
- Plasmacytoid Dendritic Cells (CD303+CD123+)
- NK cells dim (CD3-CD16+CD56+) and bright (CD3-CD16-CD56++);
- NKT cells (CD3+CD56+);
- Myeloid Dendritic cells (CD1c+ and CD141+);
- Monocyte subsets (classical CD14+CD16-, intermediate CD14+CD16+, non classical CD14+/-CD16+);
- B lymphocytes (CD19+);
- Analysis of plasma cytokines (TNFalpha, TGFbeta, IL-6, IL-10) by ELISA;
- IFN signature: real-time PCR on mRNA from PBMCs

A centralized evaluation of all blood and tissue samples collected will be performed at the Department of Molecular and Translational Medicine, Oncological-Immunological Experimental Section, University of Brescia.

Follow up of all subjects enrolled will be conducted according to clinical practice, with periodic visits and instrumental assessments. Survival status of the patients and possible other treatments performed will be collected for at least 24 months.

Plasma and mRNAs will be stored at the Department of Molecular and Translational Medicine, Oncological-Immunological Experimental Section, University of Brescia. All samples will be identified by a specific numerical code.

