10.1 Sample size calculations

To test the Hazard Ratio between Group0 (patients with ALC less than 500 cells/mL) and Group1 (patients with ALC greater than 500 cells/mL) of 0.3 with type I error rate of 5% and power of 80%, we need a minimum of 23 total events which in our hypothesis of median survival time in Group 0 equal to 18 months, 5% censoring rate and whole duration of the study of 4 years correspond to 42 patients, 17 in the Group0 and 25 in the Group1..

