10.2 Statistical plan

Disease-free survival and overall survival in treated patients will be analyzed with a Cox proportional hazards regression, first univariable and then multivariable.

Change between T0 (28 days after RT) and T1 (24 months) in secondary endpoints, all recorded as continuous variables, will be modelled using linear mixed models (or GEE), accounting for within patient repetition. The interaction between time and ALC status will be the effect of interest. All models will adjust for potentially confounding clinical variables.

.11.SCHEDULE OF EVALUATION

Evaluation	Screening	TREATMENT PERIOD			Follow up at 24 months
		Day -1	RT treatment (period 0)	Day +28 (from the end of RT)	
Informed consent	X				
Inclusion/exclusion criteria	X				
Medical history	X				
ECOG PS Status	X				
Vital signs	X				
Evaluation of high-risk factors for recurrence	X				
RT treatment			X		
RT characteristics (site-volume-dose)			X	X	
Immune markers *		X		X	
Molecular profile		X			
Outcomes: DFS and OS					X

*circulating T cells CD3+CD8+ and CD3+CD4+

absolute lymphocyte (ALC) count and neutrophil counts (ANC) and neutrophil/lymphocyte ratio (NLR)

Treg lymphocytes, defined as CD4+CD25+FOXP3+ or CD4+CD25hi+CD39+ cells.

Naïve/Memory T lymphocytes CD4+ and CD8+ (defined as CD45RA/CD45RO)

myeloid-derived suppressor cells, defined as cells expressing Lin-neg (CD3, CD14, CD15, CD19, CD56) /HLA-DR-/CD33+/CD11b+ in either a “lymphocyte” (small FSCxSSC) gate, or in a “monocyte” (larger FSCxSSC) gate, and as HLA-DR+/lo CD14+ cells in a large gate.

Plasmacytoid Dendritic Cells (CD303+CD123+)

NK cells dim (CD3-CD16+CD56+) and bright (CD3-CD16-CD56++);

NKT cells (CD3+CD56+);

Myeloid Dendritic cells (CD1c+ and CD141+);

Monocytes subsets (classical CD14+CD16-, intermediate CD14+CD16+, non classical CD14+/-CD16+);

B lymphocytes (CD19);

Analyses of plasma cytokines (TNFalpha, TGFbeta, IL-6, IL-10) by ELISA;

IFN signature: real-time PCR on mRNA from PBMCs

Any other treatment performed by the patient in case of progression will be collected and reported in the CRF.

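### Section 10.2 promises confounder adjustment without saying how covariates enter; entered as main effects, patient-fixed confounders would leave the time-by-ALC contrast in immune change essentially unadjusted

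*Combined protocol and SAP*

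**What the plan says.** Section 10.2 states that the continuous secondary endpoints "will be modelled using linear mixed models (or GEE), accounting for within patient repetition". It continues: "The interaction between time and ALC status will be the effect of interest". The whole provision for confounding is one sentence: "All models will adjust for potentially confounding clinical variables". No covariate is named, and nothing says whether covariates enter as main effects or together with time.

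Section 6 has the markers "assessed at baseline (day -1) before adjuvant RT and at day 28 (+/- 3) after RT completion"; sections 2.2.2 and 4.1 and the schedule of evaluation agree. That makes two samples per patient. Section 10.2, however, labels the modelled interval differently: "Change between T0 (28 days after RT) and T1 (24 months) in secondary endpoints".

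Sections 2.2.1 and 2.2.2 also plan comparisons of change by irradiated site, volume, dose, nodal irradiation and toxicity, and by immune status: "Changes in immune population cells in the immunosuppressed patient subgroup in comparison with non-immunosuppressed patients". No model term is written for any of these.

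**The concern.** With two samples per patient, a time-by-group coefficient is the difference between groups in mean within-patient change. A characteristic that does not vary within a patient cannot explain that change unless its own effect is allowed to differ between the two times. The confounders one would choose here are of this kind. Medical history, performance status and risk factors are recorded once at screening, and site, volume and dose describe one course of radiotherapy. Adding them as main effects satisfies the wording of the adjustment sentence but leaves the estimate where it was.

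Confounding is plausible on the protocol's own account. Section 1.3 says that, in other cancers, the worse outcomes seen with post-radiation blood-count changes were related to dose, volume and site of irradiation, so these may differ between ALC groups and also drive change in other cell populations. Section 3.1 gives immunosuppressed patients an additional entry route ("desmoplastic or infiltrative tumors in the setting of chronic immunosuppression"), so their case mix may differ from that of other patients. At stake is whether a difference in immune change published as adjusted has been adjusted at all.

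**Working it through.** **Plan figures.** The plan gives no number for the immune-change models. Its one computed figure, 23 events, concerns DFS and has no bearing here; it reproduces as (1.960 + 0.842)² / [(17/42)(25/42)(ln 0.3)²] = 22.5, rounded up to 23. The only input taken from the plan is group size: "correspond to 42 patients, 17 in the Group0 and 25 in the Group1".

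**Algebra.** Let t be 0 or 1 for the two samples, g the group, x a patient-fixed confounder and u the patient effect. With x as a main effect:

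y = b0 + b1·t + b2·g + b3·t·g + c·x + u + e

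The within-patient change is D = b1 + b3·g + (e1 − e0). Both c·x and u have dropped out, so with complete pairs the estimate of b3 is mean D in one group minus mean D in the other, whether or not x is in the model. Adding a term d·t·x gives D = b1 + b3·g + d·x + (e1 − e0), and b3 is then adjusted for x. Without that term, the bias in b3 is d times the difference between groups in mean x.

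**Check with 17 + 25 patients, 150 simulated trials.** Assumed: true interaction 0, x one unit higher in the low-ALC group, d = −1. Expected bias for high minus low ALC: −1 × (0 − 1) = +1.

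| Model (complete pairs) | Mean interaction | Rejections at 5% (mixed model / GEE) |
|---|---|---|
| Unadjusted | 0.984 | 65% / 65% |
| x as main effect | 0.984 | 65% / 65% |
| x by time | −0.010 | 3% / 5% |

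The first two estimates differed by at most 2e-14 in any trial. A separately simulated dataset of the same size gave −0.5204 (SE 0.283) both without and with the main effect, and −0.134 once covariate-by-time was added. The 65% reflects deliberately severe confounding and is not a forecast for this study.

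**Where the cancellation is not exact.** The second sample was made missing more often at high x, with base probabilities of 20% and 40%. The mixed-model main-effect estimate then differed from the unadjusted one by 0.02 and 0.04 on average (maximum 0.16 and 0.29). The bias stayed at 0.90 and 0.86, against about 0.00 and −0.02 with covariate-by-time. A time-varying covariate moved the main-effect estimate by 0.10 on average (maximum 0.51).

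**Size under other inputs.** These inputs are assumed, for the immunosuppression contrast fitted with the same type of model: 10 of 42 patients immunosuppressed, nodal irradiation as the confounder, 6,000 trials per setting.

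| Nodal irradiation, immunosuppressed vs others | Shift in change (SD) | False positives, main effect only |
|---|---|---|
| 20% vs 47% | 0.25 to 0.5 | about 5-6% |
| 20% vs 47% | 1 | about 10% |
| 20% vs 47% | 2 | about 17-18% |
| 30% vs 47% | 1 | about 7% |
| 30% vs 47% | 2 | about 9-10% |
| 40% vs 47% | 0.25 to 2 | about 5-6% |

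With covariate-by-time the rate is about 5%. Hand check at 20% vs 47% and 1 SD: bias = 1 × (0.47 − 0.20) = 0.27 SD. The variances of change are 1 + 0.20 × 0.80 = 1.16 and 1 + 0.47 × 0.53 = 1.25, so SE = √(1.16/10 + 1.25/32) = 0.39. The ratio is 0.69, which gives a rejection rate near 10%.

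**The case against.** The strongest reply is that the fault is not written in the plan. Section 10.2 never says main effects only, and a statistician who used covariate-by-time terms or a regression of change would comply with it fully. That stands. What can be shown is that the plan is silent on the form, and that the commonest way of filling the silence has no effect on this contrast.

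A reader might infer that every between-group contrast in immune change will go unadjusted. The documents do not support this. An interaction is written for ALC status only, and the other comparisons in sections 2.2.1 and 2.2.2 have no stated model. They share the problem only if fitted in the same way. Nor is it right that main effects can never move the interaction: exact cancellation needs complete pairs, patient-fixed covariates and an identity link.

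The magnitude can also be challenged. Every confounding input is assumed, and with weak confounding the inflation is close to nothing. Nothing in the documents says that immunosuppressed patients receive smaller fields or less nodal irradiation; they may enter by all the other routes too.

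Finally, site, volume, dose, nodal irradiation and immunosuppression are themselves factors of interest. Whether each should be adjusted for the others depends on the question being asked, so one universal covariate list would be a preference rather than a correction.

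**Conclusion.** The point holds as a gap in specification that has a definite consequence. If patient-fixed confounders enter as main effects, the time-by-ALC contrast keeps its unadjusted value, exactly with complete pairs and an identity link and nearly so with some samples missing, yet would be reported as adjusted. That result is algebra and does not depend on the assumed inputs.

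The size does depend on them. In the nodal-irradiation scenarios the false-positive rate lies between about 5-7% and about 17-18%. This is an illustration and not a bound, since more severe confounding gives more. The documents give no figure from which to say where this study would fall.

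Only the secondary immune-change analyses are concerned. In the primary DFS Cox model a main effect does adjust the group comparison. The change should be made, but it does not threaten the primary result.

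**What to change.** Replace the adjustment sentence in section 10.2, for the immune-change models, with wording such as: each pre-specified confounder enters together with its interaction with time; where both samples are available for all patients this is equivalent to regressing within-patient change on the factor of interest and the confounders.

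Name a short covariate set for each contrast, drawn from nodal irradiation or irradiated volume, head-and-neck site, and immunosuppression, leaving out whichever is the factor under study. State a model for each comparison in sections 2.2.1 and 2.2.2, not only for ALC status.

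In the same paragraph, reconcile the time points. Section 10.2 models day 28 to 24 months, whereas markers are sampled at day −1 and day 28 and none at 24 months, so the model cannot be fitted as worded. Rewriting the adjustment sentence alone would not cure that.

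No new data are needed. The cost is two or three degrees of freedom out of 42 patients and wider intervals where the factors overlap. That loss of precision should be accepted openly, and it is a reason to keep each covariate set short.
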